2.2 Analysis sets

If the starting dose is different from the assigned dose level due to co-administration of ruxolitinib with strong CYP3A4/CYP2C9 inhibitors, these subjects will be included under the assigned dose level and considered that they have received the full assigned dose. This applies to Full Analysis Set, Safety Set, and Pharmacokinetic analysis set as described below.

If the treatment formulation (tablet/liquid) changed during treatment, the subject will be considered under the formulation she/he started treatment. Nevertheless, a change in formulation will be flagged and may be considered for PK analyses.

The **Full Analysis Set** (FAS) comprises all subjects to whom study treatment has been assigned and who received at least one dose of study treatment.

The **Safety Set** includes all subjects who received at least one dose of study treatment. Subjects will be analyzed according to the study treatment received, where treatment received is defined as the assigned dose level of ruxolitinib if the subject took at least one dose of that treatment or the first dose level received if the assigned dose level was never received.

The **Pharmacokinetic analysis set** (PAS) includes all subjects who provide at least one evaluable PK concentration. For a concentration to be evaluable, subjects are required to:

- Take the dose of ruxolitinib prior to PK sample

- For post-dose samples on Cycle 1 Day 1: do not vomit within 2 hours after the dosing of ruxolitinib
- For pre-dose samples: have the sample collected before the next dose administration of ruxolitinib; do not vomit within 2 hours after the previous dosing of ruxolitinib prior to sampling.

The **Listing only Set** contains only those patients who are not eligible for efficacy analyses due to PD “Patient enrolled and treated beyond local regulatory requirements”. These patients will also not be included in safety summary analyses, but all safety data will be provided in listings, separately from the listings of all other patients.

Patient Classification:

Patients may be excluded from the analysis populations defined above based on the protocol deviations entered in the database and/or on specific patient classification rules defined in [Table 2-3](#).

Patients with protocol deviation OTH12 “Patient enrolled and treated beyond local regulatory requirements” will only be included in the “Listing only Set” and not in any other analysis set.

Table 2-3 Patient classification based on protocol deviations and non-PD criteria

Analysis set	Protocol deviations leading to exclusion	Non protocol deviation leading to exclusion
FAS	INCL01A, OTH12	Not applicable
Safety Set	INCL01A, OTH12	No dose of study treatment
PK Analysis Set	INCL01A, OTH12, TRT01/ TRT02	No dose of ruxolitinib, No evaluable PK concentration
Listing only Set	OTH12 (include only patients with this PD)	Not applicable

INCL01A - Written informed consent was not obtained

OTH12 - Patient enrolled and treated beyond local regulatory requirements

TRT01 - Starting dose of study drug (ruxolitinib) not per protocol-defined age-based schedule (Group 1 and 2).

TRT02 - Starting dose of study drug (ruxolitinib) not per protocol-defined age-based schedule (Group 3 and 4).

Withdrawal of Informed Consent

Any data collected in the clinical database before a patient signed informed consent or after a patient withdraws informed consent from all further participation in the trial, will not be included in the analysis. The informed consent data and the date on which a patient withdraws full consent is recorded in the eCRF.

2.2.1 Subgroup of interest

Efficacy

Subgroup analyses for efficacy endpoints will not be repreated for the final CSR.

The primary efficacy endpoint will be summarized by the following subgroups:

- Age group (please refer to [Section 1.1](#) for the definition)
- Age group and formulation (tablet vs liquid)
- Treatment Naive cGvHD vs SR-cGvHD
- Region EU+ROW except Turkey / Turkey / Asia excl. Japan / Japan
Note: ROW includes US, Canada, Australia and other countries (e.g. Russia).
- Chronic GvHD severity at baseline, moderate vs. severe (as reported on the staging CRF and not from the GvHD Disease History page).

No formal statistical test of hypotheses will be performed for the subgroups, only point estimate of the treatment effect and 90% confidence intervals will be provided.

Safety

Key safety analyses will be repeated on the Safety Set in the following subgroups:

- Age group (please refer to [Section 1.1](#) for the definition)
- Treatment-naive cGvHD vs. SR-cGvHD
- Region EU+ROW except Turkey / Turkey / Asia excl. Japan / Japan
- Chronic GvHD severity (moderate vs. severe)

For the final CSR safety subgroup analyses will be repeated for age groups and treatment-naïve cGvHD vs. SR-cGvHD only.

The objective for carrying out these subgroup analyses is to identify potential safety issues that may be limited to or more commonly observed in a subgroup of patients. The following summaries will be presented by subgroup:

- Overview of adverse events
- Serious AEs, irrespective of causality, by primary system organ class and preferred term
- On-treatment deaths, by primary system organ class and preferred term

These additional analyses will be provided only by age groups and by treatment-naïve vs SR cGvHD:

- AEs, irrespective of causality, by primary system organ class and preferred term
- AEs with suspected relationship to investigational treatment, by primary system organ class and preferred term
- Serious AEs with suspected relationship to investigational treatment, by primary system organ class and preferred term
- Overview of adverse events of special interests

Japanese patients

Analyses on the subgroup of Japanese patients will not be repeated for the final CSR.

Subgroup analyses may also be performed for the patients treated in Japan. No selection will be done on the basis of ethnicity, the purpose being to evaluate the population of patients living in Japan, not a specific ethnic set of patients. The analysis will be done the same way as in region subgroup specified above.

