1.1 Study design

This open-label, single-arm, Phase II multi-center study will investigate the activity, pharmacokinetics and safety of ruxolitinib added to the subject's immunosuppressive regimen among infants, children, and adolescents aged ≥ 28 days to < 18 years old with either moderate

to severe treatment-naïve cGvHD or SR-cGvHD. Approximately 42 subjects will be enrolled in this study. Subjects will be grouped according to their age as follows: Group 1 includes subjects ≥ 12 y to < 18 y, Group 2 includes subjects ≥ 6 y to < 12 y, Group 3 includes subjects ≥ 2 y to < 6 y, and Group 4 includes subjects ≥ 28 days to < 2 y. Subjects will remain in the age group throughout the study based on the age at the time of start of treatment. Enrollment initiation into the youngest age group, Group 4, will be subject to the availability of data in this age group from study [CINC424F12201], as well as a review of available PK, safety, and clinical activity data generated from Groups 1 to 3 in the current study, in consultation with the data monitoring committee (DMC) and a final decision by the Sponsor. At least 5 evaluable subjects per Group are needed for the primary analysis in Groups 1, 2 and 3. No minimum number of evaluable subjects are needed in Group 4.

As shown in [Figure 1-1](#), after a screening period from Day -28 to Day -1, eligible subjects will begin the investigational treatment (ruxolitinib) on Cycle 1 Day 1 and will be treated for up to a maximum of 3 years (39 cycles/week 156) or until early discontinuation. Subjects who discontinue ruxolitinib for any reason earlier than 39 cycles will be followed every 6 months until 3 years from their first dose of ruxolitinib is reached. Subjects who tapered off ruxolitinib and all immunosuppressive therapy due to achieving a CR or PR will continue to follow the currently assigned Visit Evaluation Schedule (Table 8-1), including all safety and efficacy assessments.

Figure 1-1 **Study Design**

Refer to protocol Section 8.2.1 for details of the treatment period study visits. All subjects continuing to receive ruxolitinib treatment benefit following 3 years of treatment will be given the possibility to continue ruxolitinib outside the study, from another source, where permitted in accordance with local laws and regulations.

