2.1 Data analysis general information

The interim and final analysis will be performed by Novartis. SAS version 9.4 or later and/or R version 3.0.2 or later will be used to perform all data analyses and to generate tables, figures and listings.

The analysis cutoff date for the interim analysis of study data will be established when all patients have completed 1 year of treatment or discontinued earlier. The analysis cutoff date for the final analysis of study data will be established when all patients have completed the study.

All statistical analyses will be performed using all data collected in the database up to the data cutoff date. All data with an assessment date or event start date (e.g. vital sign assessment date or start date of an adverse event) prior to or on the cutoff date will be included in the analysis. Any data collected beyond the cutoff date will not be included in the analysis and will not be used for any derivations.

All events with start date before or on the cutoff date and end date after the cutoff date will be reported as 'ongoing'. The same rule will be applied to events starting before or on the cutoff date and not having documented end date. This approach applies, in particular, to adverse event and concomitant medication reports. For these events, the end date will not be imputed and therefore will not appear in the listings.

General analysis conventions

Pooling of centers: Unless specified otherwise, data from all study centers will be pooled for the analysis. Due to expected small number of patients enrolled at centers, no center effect will be assessed.

Qualitative data (e.g., gender, race, etc.) will be summarized by means of contingency tables; a missing category will be included as applicable. Percentages will be calculated using the number of patients in the relevant population or subgroup as the denominator.

Quantitative data (e.g., age, body weight, etc.) will be summarized by appropriate

descriptive statistics (i.e. mean, standard deviation, median, minimum, and maximum).

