2. On-treatment period: from day of first dose of ruxolitinib to 30 days after date of last actual administration of assigned treatment.
3. ***post-treatment period***: starting at Day 31 after last administration of ruxolitinib.

Safety summaries (tables, figures) include only data from the on-treatment period with the exception of baseline data which will also be summarized where appropriate (e.g. change from baseline summaries). In addition, a separate summary for death including on-treatment and post-treatment deaths will be provided. In particular, summary tables for adverse events (AEs) will summarize only on-treatment events, with a start date during the on-treatment period (***treatment-emergent*** AEs).

However, all safety data (including those from the post-treatment period) will be listed and those collected during the pre-treatment and post-treatment period will be flagged. In analyses for the safety disclosure, all AEs collected in the post-treatment period will be included and reported separately.

Subjects who taper off ruxolitinib due to achieving a CR or PR continue efficacy and safety assessments until their EoT visit which may be only after Cycle 39 unless the subject discontinues from study earlier. Safety data from these patients collected after the last study drug intake date + 30 days and before EoT visit will not be included in any safety analyses based on the on-treatment period as defined above. Nevertheless, these data will be listed and flagged in all listings (AEs, lab, vital signs). Subject who tapered off ruxolitinib are identified as they have reason "responder" for ruxolitinib permanent discontinuation on the exposure CRF.

For subjects who tapered off study treatment and later re-started ruxolitinib treatment after a cGvHD recurrence, the on-treatment period is from date of first dose of ruxolitinib to very last dose + 30 days including the period without treatment, which are collected in the database as dose interruption. Safety data (e.g. AEs, labs) collected during this period without treatment will be included in the summary tables as treatment emergent events.

Windows for multiple assessments

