The duration of exposure to investigational treatment in patient-years is a total of the duration of exposure to investigational treatment in years from all the patients in the Age group.

Duration of exposure to systemic corticosteroid

Duration of exposure to systemic corticosteroid treatment (days) = (last date of exposure to systemic corticosteroid) – (date of first administration of systemic corticosteroid) + 1.

Duration of exposure to systemic corticosteroid in patient-years

The duration of exposure to systemic corticosteroid in patient-years is a total of the duration of exposure to systemic corticosteroid in years from all the patients in the Age group.

Cumulative dose

The **planned cumulative dose** for ruxolitinib refers to the total planned dose per protocol up to the last dose date.

The **actual cumulative dose of ruxolitinib** refers to the total actual dose of ruxolitinib as documented in the Study Treatment eCRF.

For patients who did not take any drug the cumulative dose is by definition equal to zero.

Dose intensity and relative dose intensity of ruxolitinib

Subjects receive ruxolitinib in doses twice a day (bid). For purposes of reporting dose intensity, a summary over the dose by day (total daily dose) is provided.

Dose intensity (DI) of ruxolitinib for patients with non-zero duration of exposure is defined as follows:

$DI \text{ (mg / day or mg/m}^2\text{/day)} = \text{Actual cumulative dose (mg or mg/m}^2\text{) of ruxolitinib / Duration of exposure to ruxolitinib (days)}$.

In case the study includes subjects who taper off ruxolitinib and later re-start ruxolitinib treatment due to cGvHD recurrence, the duration of exposure excluding “taper off periods” will be used as denominator for dose intensity.

For patients who did not take any drug, the DI is by definition equal to zero.

Planned dose intensity (PDI) is defined as follows:

$PDI \text{ (mg/day or mg/m}^2\text{/day)} = \text{Planned Cumulative dose (mg or mg/m}^2\text{) / Duration of exposure (days)}$.

The PDI of ruxolitinib with daily dose schedule is according to protocol for the three age groups:

- Age group 1: 20 mg/day
- Age group 2: 10 mg/day
- Age group 3: 8 mg/m²/day using the baseline BSA

Relative dose intensity (RDI) is defined as follows:

$RDI = DI \text{ (mg / day or mg/m}^2\text{/day)} / PDI \text{ (mg / day or mg/m}^2\text{/day)}$.

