2.8.1 Adverse events (AEs)

For reporting of AEs, the overall observation period will be divided into mutually exclusive categories, including pre-treatment, on-treatment, post-treatment periods as defined in [Section 2.1.1](#).

AE summaries will include all Aes occurring (new or worsening) during on-treatment period. All Aes collected in the AE eCRF page will be listed along with the information collected on those Aes e.g. AE relationship to study drug, AE outcome etc. Aes with start date outside of on-treatment period will be flagged in the listings.

Aes will be summarized by number and percentage of patients having at least one AE, having at least one AE in each primary system organ class (SOC) and for each preferred term (PT) using MedDRA coding. A patient with multiple occurrences of an AE will be counted only once in the respective AE category. A patient with multiple CTCAE grades for the same preferred term will be summarized under the maximum CTCAE grade recorded for the event. AE with missing CTCAE grade will be included in the ‘All grades’ column of the summary tables.

In AE summaries, the primary system organ class will be presented alphabetically, and the preferred terms will be sorted within primary SOC in descending frequency. The sort order for the preferred term will be based on the descending frequency in the ruxolitinib arm.

The following adverse event summaries will be produced by group; overview of adverse events and deaths, Aes by SOC and PT, summarized by relationship (all Aes and Aes related to study treatment), seriousness (SAEs and non-SAEs), leading to treatment discontinuation, leading to dose interruption/adjustment, and leading to fatal outcome.

In addition, summary table and listing will be provided for COVID-19 related Aes.

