2.8.1.2 Adverse events of special interest / grouping of AEs

An adverse event of special interest is a grouping of adverse events that are of scientific and medical concern specific to compound ruxolitinib. These groupings are defined using MedDRA terms, SMQs (standardized MedDRA queries), HGLTs (high level group terms), HLT (high level terms) and/or PTs (preferred terms). Customized SMQs (CMQs) may also be used. A CMQ is a customized group of search terms which defines a medical concept for which there is no official SMQ available or the available SMQ does not completely fit the need. It may include a combination of single terms and/or an existing SMQ, narrow or broad.

For each AESI, number and percentage of patients with at least one event of the AESI occurring during on-treatment period will be summarized. Summaries of AESIs will be provided by group (specifying grade, SAE, relationship, leading to treatment discontinuation, leading to dose adjustment/interruption, hospitalization, death etc.).

A listing of all grouping levels down to the MedDRA preferred terms used to define each AESI will be generated.

In addition to summarizing infections by CTCAE grade, they will also be summarized using infection severity (protocol Appendix 1) for the on-treatment period. A listing of infection with infection severity will be generated and the events with start date outside of on-treatment period will be flagged.

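### Final-CSR safety subgroup tables compare crude percentages of patients with an event over on-treatment windows that can run from weeks to 3 years, with no exposure measure beside them for treatment-naive versus SR-cGvHD

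*SAP*

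**What the plan says.** SAP 2.2.1 (Safety) states that the subgroup analyses are meant to "identify potential safety issues that may be limited to or more commonly observed in a subgroup of patients". For the final CSR only two groupings remain: age group, and treatment-naive versus SR-cGvHD. The tables are the AE overview, AEs and SAEs (all and suspected related), on-treatment deaths, and the overview of AEs of special interest (AESIs).

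The measure is set elsewhere in the SAP:

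- 2.8.1: "Aes will be summarized by number and percentage of patients having at least one AE".
- 2.8.1.2, for AESIs: "number and percentage of patients with at least one event of the AESI occurring during on-treatment period will be summarized".
- 2.1, for the denominator: "Percentages will be calculated using the number of patients in the relevant population or subgroup as the denominator".

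Time at risk is not fixed. Patients "will be treated for up to a maximum of 3 years (39 cycles/week 156) or until early discontinuation" (SAP 1.1), and the on-treatment period runs from first dose "to 30 days after date of last actual administration of assigned treatment" (SAP 2.1.1). For patients who taper off and later restart, 2.1.1 adds: "Safety data (e.g. AEs, labs) collected during this period without treatment will be included in the summary tables as treatment emergent events".

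SAP 2.4.1 does compute time on drug: "The duration of exposure to investigational treatment in patient-years is a total of the duration of exposure to investigational treatment in years", summed over the patients in each age group. Duration of ruxolitinib exposure is also by age group. Corticosteroid exposure is additionally split by treatment-naive versus SR (SAP 2.4.2.3); ruxolitinib exposure is not.

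The one time-based adverse event analysis is the cumulative incidence of grade 3 or higher infection (SAP 2.8.4.3), by age group if numbers allow and by treatment-naive versus SR. Death and discontinuation of study treatment are competing risks.

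**The concern.** A percentage of patients with at least one event rises with the time over which events are counted. Here that time depends on outcome. Protocol 6.1.5 has patients without benefit stop ruxolitinib and lets responders taper from Cycle 7 Day 1, and Protocol 9.1.1 makes lack of efficacy a reason for stopping. If treatment-naive and SR patients, or the age groups, leave treatment at different times, their percentages will differ even when the event rate is the same.

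The error can go either way. A subgroup that stays on drug can look more toxic than it is. A true excess in a subgroup that stops early can go unseen. For age group, the reader can at least compare the percentages with the exposure tables. For treatment-naive versus SR, no ruxolitinib exposure summary is planned.

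**Working it through.** **The plan's own figure.** There is none on this point. The only design calculation (SAP 3) concerns the response rate and does not bear on safety.

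**Inputs from the documents.** Maximum treatment is 3 years (SAP 1.1). The window ends 30 days after last dose (SAP 2.1.1), and 30/365.25 = 0.082 years. Age groups hold 22, 17 and 7 patients (Protocol, Amendment 2 summary).

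**Assumed inputs.** Event rates and subgroup exposures are not in the documents. Rates of 0.2 to 0.6 first events per patient-year and exposures of 0.5 to 3 years are illustrations, with every patient in a subgroup given the same exposure.

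**Step 1. Same constant rate, different exposure.** Expected crude percentage = 1 − exp[−rate × (exposure + 0.082)].

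| Rate per patient-year | 0.5 years | 2 years | 3 years |
|---|---|---|---|
| 0.5 | 25.3% | 64.7% | 78.6% |
| 0.2 | 11.0% | 34.1% | 46.0% |

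For example, 1 − exp(−0.5 × 0.582) = 25.3%. The underlying rate is identical along each row.

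**Step 2. A real excess hidden.** Subgroup A has 0.6 per patient-year and 0.5 years of exposure: 1 − exp(−0.6 × 0.582) = 29.5%. Subgroup B has 0.3 per patient-year and 1.5 years: 1 − exp(−0.3 × 1.582) = 37.8%. The subgroup with twice the rate shows the lower percentage.

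**Step 3. Does the infection analysis close the gap?** Let λ be the infection rate and d the rate of leaving the on-treatment period, with d = ln 2 / median on-treatment time. Cumulative incidence at time t = λ/(λ + d) × [1 − exp(−(λ + d)t)]. Take λ = 0.3 in both subgroups.

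| Median on-treatment time | At 6 months | At 36 months |
|---|---|---|
| 0.5 years (d = 1.386) | 10.1% | 17.7% |
| 2 years (d = 0.347) | 12.8% | 39.7% |

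The early estimates are close. The late ones depend on time on drug, as the crude percentage does.

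**Step 4. Would a rate alone be safe?** Assume both subgroups share a front-loaded hazard: 2 per patient-year for 3 months, then 0.2. Expected time at risk per patient = (1 − e^−0.5)/2 + e^−0.5 × [1 − exp(−0.2 × (window − 0.25))]/0.2.

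| | Exposure 0.5 years | Exposure 2 years |
|---|---|---|
| Cumulative hazard | 0.5 + 0.2 × 0.332 = 0.566 | 0.5 + 0.2 × 1.832 = 0.866 |
| Crude percentage | 43% | 58% |
| Time at risk per patient | 0.392 years | 1.127 years |
| Rate per 100 patient-years | 110 | 51 |
| First 6 months: 1 − exp(−0.55) | 42% | 42% |

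The crude percentage overstates the longer-exposed subgroup 1.3-fold (58/43). The rate overstates the shorter-exposed one 2.1-fold (110.4/51.4). Only the common window shows them equal, and it does so because both subgroups are exposed for the whole 6 months.

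**Step 5. Precision.** For the group of 7, assume 0.3 per patient-year and 0.5 years of exposure. About 1.1 patients with an event are expected in 3.7 patient-years. One event gives an exact Poisson 95% CI of about 0.7 to 149 per 100 patient-years.

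**The case against.** Four points can fairly be made against this concern.

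- **Other analyses exist.** A reader might infer that crude percentages are the only safety measure in the plan. They are not. Grade 3 or higher infection has a cumulative incidence analysis by both retained subgroups, with estimates at 1, 2 and 6 months, where unequal exposure matters least. All deaths, including post-treatment deaths, are summarised by age group (SAP 2.8.2), and early discontinuers are followed for survival to 3 years from first dose (Protocol 9.1.1). This stands. But the infection analysis covers one event type, and Step 3 shows that it still depends on time on drug at later time points.
- **Exposure is already shown by age group.** This also stands, and it leaves treatment-naive versus SR as the plainer gap.
- **A rate can be worse than a percentage.** It presumes a roughly constant hazard. The randomised steroid-refractory acute GvHD study described in Protocol 1.1.2.1.2 had thrombocytopenia in 33% of ruxolitinib patients by day 28, so early clustering is plausible for at least one key event. Step 4 confirms the point. It rules out making the rate decisive.
- **The tables are descriptive.** No between-subgroup test is planned, and a group of 7 supports little inference. That limits how much is at stake. It does not remove the problem, since the stated purpose is to find events that are more common in a subgroup.

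**Conclusion.** The concern holds for the subgroup tables listed in SAP 2.2.1. Their purpose is comparative, their measure ignores time at risk, and that time can run from weeks to about 3 years. Under an assumed equal constant rate, crude percentages could differ by roughly 40 percentage points at 0.5 per patient-year (25.3% versus 64.7% for 0.5 versus 2 years), or by 23 points at 0.2 (11.0% versus 34.1%).

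Three stronger readings are not supported. The documents do not show that exposure differs between subgroups, so neither the size nor the direction of any distortion is known. They do not show that the stated aim is out of reach: counts and percentages remain usable for screening once exposure is shown beside them. Nor do they support replacing percentages with rates, because the gap in percentages is smaller for early-onset events and the rate can then create a false excess in a short-exposure subgroup.

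This is a worthwhile, inexpensive improvement to the safety display. It does not touch the primary analysis.

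**What to change.** 1. Summarise duration of ruxolitinib exposure and patient-years by treatment-naive versus SR-cGvHD as well as by age group.
2. In the AE overview, SAE and AESI subgroup tables, keep the crude percentage and add two columns. The first is the exposure-adjusted rate per 100 patient-years: patients with a first event divided by time to first event or to the end of the on-treatment period, with an exact Poisson 95% CI. The second is the incidence in a common early window, such as the first 6 months.
3. Define time at risk by the on-treatment period, not by the exposure definition that leaves out the drug-free gap. Events in that gap are counted as treatment-emergent, so numerator and denominator then match for patients who restart.
4. State in the SAP that the crude percentage, the early-window incidence and the rate will be read together before an event is called more common in a subgroup, and that none of the three decides alone.

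The cost is extra columns and one exposure table, using dates already collected. Intervals will be wide in the group of 7. The early window compares like with like only as far as patients stay on treatment through it, so the number still on treatment at its end should be shown.
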